Evaluable patients' population (evaluable per protocol population, EPP): consists of all patients from the FAS without any major inclusion/exclusion violation, major dosing violation as defined for phase II part 1, or major protocol conduct violation who were dosed with IMP(s) according to the treatment allocated at randomization and have at least one baseline and one post-baseline evaluable CT-scan at week 6 after start of study treatment with a best overall response assessment different from 'Unknown' according to RECIST 1.1 evaluation criteria.

Sample size:

Phase Ib of the study: there will be no formal sample size for the phase Ib of the study. The dose escalation part of the trial follows the methodology of a 3+3 cohort design for dose-finding studies in oncology. Depending on the observed DLTs, a maximum of 12 evaluable patients will be included in this part of the study.

Phase II part 1: a Simon's two-stage design will be used. The null hypothesis for response rate H_0 is set at 10% corresponding to the response rate observed in second line patients, the alternative hypothesis of efficacy is set at $H_A=25\%$, the type I error α is set at 5% one sided, the type II error β is set at 20% (power=80%). Under these hypotheses and applying a minimax two-stage Simon design, enough patients will be treated to obtain 22 evaluable patients as a first stage. If at least 3/22 patients are considered responders, the enrolment will be continued, otherwise it will be stopped. In the initial design and at the second stage enough patients should have been treated to obtain at least 40 evaluable patients in total. The study would have been considered positive with at least 8/40 responders. With a hierarchical strategy on the final analysis, a subgroup analysis performed in oropharyngeal SCCHN patients and with a null hypothesis for response rate (H_0) set at 10% and the alternative hypothesis of efficacy set at $H_A = 35\%$, 18 oropharyngeal SCCHN patients would have been needed to reach a power of 81% and actual alpha at 2.8%. This analysis would have been considered positive with at least 5 responders among the 18 SCCHN patients. The second stage of the Simon's design has not been done following the decision to exclude oropharyngeal SCCHN and to change to a randomized controlled two-arms study (phase II part 2).

Phase II part 2:

- For the cohort of patients without liver metastases at baseline, an adaptive sample size re-estimation is applied: based on the results obtained in phase II part 1, the hypothesis for median PFS in the combination arm (TG4001 with avelumab) is set at 4.5 months. The hypothesis for median PFS in the monotreatment arm (avelumab alone) is set at 2 months. The type I error α is set at 5% one sided, the type II error β is set at 5%.

A two-stage group sequential design will be used with logrank test and boundary for efficacy at $\alpha=0.00001$ and Conditional Power (CP) at 10% for futility.

At the interim analysis, a first test for efficacy is performed on 37 PFS events at a level of significance of 0.000001. A sample size of 50 patients is estimated at time of the Interim Analysis.

Otherwise, the following decision rules are applied based on CP using CHW (Cui, Hung and Wang) approach.

- Favorable zone: If the interim results are sufficiently favorable corresponding to a CP of more than 90%, final analysis will be performed on 74 PFS events corresponding to an estimated sample size of 80 patients.
- Promising zone: If the interim results are equivalent to a CP between 90% and 30%, the sample size will be recalculated according to the median PFS observed in the two arms with a cap of 2 times the initial number of events.

- Unfavorable zone: If the interim results are not favorable corresponding to a CP between 30% and 10%, the trial may continue up to the initial sample size of 80 patients or could be stopped.
- Futility zone: If the interim results are futile corresponding to a CP lower than 10%, the trial will be stopped for futility at the interim analysis.

[figure not shown]
Assuming uniform enrollment with 3 patients per month, an average of 136 patients are needed to observe 124 PFS events. Assuming a 5% lost to follow-up or withdrawal of consent rate, a total of 142 patients should be randomized to the 2 treatment arms in a 1:1 ratio (71 patients in each treatment arm).

[REDACTED]

[REDACTED]

[REDACTED]

[REDACTED]

- For the cohort of patients with liver metastases at baseline, [REDACTED]

[REDACTED]

[REDACTED]

[REDACTED]

[REDACTED]

TABLE OF CONTENTS

INVESTIGATORS / STUDY ADMINISTRATIVE STRUCTURE.....	2
DOCUMENT APPROVAL.....	3
SYNOPSIS.....	4
TABLE OF CONTENTS.....	17
ABBREVIATIONS / DEFINITION OF TERMS	21
1 INTRODUCTION.....	26
1.1. BACKGROUND AND INTRODUCTION	26
1.1.1. Human PapillomaVirus (HPV) and related diseases	26

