With an one-sided type I error α at 5%, 76 events are needed to reach a power of 95%. This should happen after around 80 patients enrolled (40 patients per arm). Assuming 5% drop-out in each arm, 84 patients will be randomized.

[figure not shown]
Due to the uncertainty on the true treatment effect and data variability, and to reduce the risk of running an underpowered study, it is considered appropriate to adopt an adaptive approach for the sample size. This will offer a mechanism to adjust the sample size in response to treatment effect and variability estimates seen at a planned interim analysis.

The interim analysis will be conducted after 37 events which will occur approximately 16 months after the inclusion of the first patient. At that time, it is estimated to have around 50 patients enrolled. Based on the results of the interim analysis, sample size re-estimation will be performed. According to simulations on CHW (Cui, Hung and Wand) approach using EAST 6.5., the proposal is as follows:

- Start with a fixed sample size calculation based on the primary endpoint.
- Based on the interim analysis result maintain or increase the sample size in order to obtain the desired power of 90%.

Conditional power will be calculated based on the interim results. Should the conditional power be in the favorable or unfavorable range the sample size and the number of events will not be adjusted and will remain at the initial sample size. Conditional power falling into the promising zone will have a sample and events increase. The regions and their implications on sample size are detailed below:

- **Favorable:** If the interim results are sufficiently favorable corresponding to a CP of more than 90%, final analysis will be performed on 74 PFS events corresponding to an estimated sample size of 80 evaluable patients. This will occur approximately 26 months after the inclusion of the first patient.
- **Promising zone:** If the interim results are equivalent to a CP between 90% and 30%, the sample size will be recalculated according to the median PFS observed in the two arms with a cap of 2 times the initial events.
- **Unfavorable zone:** If the interim results are not favorable corresponding to a CP between 30% and 10%, the trial may continue up to the initial sample size of 80 patients or could be stopped
- **Futility:** If the interim results are futile corresponding to a CP lower than 10%, the trial will be stopped for futility at the interim analysis.

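### The synopsis gives two interim efficacy thresholds, 0.00001 and 0.000001, for the same 37-event look at PFS; the effect is negligible, but the record should show one value

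*Combined protocol and SAP*

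**What the plan says.** The two statements are in the synopsis, under sample size for phase II part 2, for patients without liver metastases at baseline.

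- The sentence introducing the two-stage group sequential design specifies a log-rank test with a "boundary for efficacy at $\alpha=0.00001$ and Conditional Power (CP) at 10% for futility".
- The next paragraph, on the interim analysis, says that "a first test for efficacy is performed on 37 PFS events at a level of significance of 0.000001".

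A two-stage design has one interim look, and both sentences concern PFS in the same cohort, so they describe the same test.

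Section 10.2 gives the timing ("The interim analysis will be conducted after 37 events which will occur approximately 16 months after the inclusion of the first patient") and the conditional-power zones, but its readable text contains no efficacy boundary. Sections 3.2 and 10.4.2 contain none either. Section 10.2 defers the full adaptive method to the SAP; that detail is not in the text available for this check.

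**The concern.** The interim efficacy boundary is the prespecified threshold for stopping the primary comparison early, and it fixes the alpha spent at the first look. A protocol should give one value. Here an interim one-sided p-value between 0.000001 and 0.00001 would meet the boundary under the first sentence and miss it under the second.

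This matters for the record because the trial is open-label with an adaptive sample size, and section 3.1.3 has the IDMC evaluate efficacy at this look. The study report will have to state which boundary applied and how much alpha was spent, and the synopsis does not allow a reader to say.

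**Working it through.** **Inputs**

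- Combination arm: "the hypothesis for median PFS in the combination arm (TG4001 with avelumab) is set at 4.5 months" (synopsis).
- Control arm: "The hypothesis for median PFS in the monotreatment arm (avelumab alone) is set at 2 months" (synopsis).
- Design hazard ratio, assuming exponential PFS: 2/4.5 = 0.444.
- Overall one-sided alpha 5%, power 95%, allocation 1:1 (synopsis).
- Interim at 37 events. Initial final analysis: "final analysis will be performed on 74 PFS events corresponding to an estimated sample size of 80 patients". Information fraction 37/74 = 0.50.
- Conditional powers in section 3.2: 90% at 104 events, above 75% at 69 events.

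**1. Reproduce the plan's event count.** Freedman: events = (1.645 + 1.645)² × [(1 + 0.444)/(1 − 0.444)]² = 10.82 × 2.6² = 73.2, rounded up to 74. This matches the synopsis and does not depend on which interim boundary is used.

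**2. Convert the two levels to boundaries.** Take them as one-sided, like the overall alpha. Critical observed HR = exp(−2z/√37), with √37 = 6.083.

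| | 0.00001 | 0.000001 |
|---|---|---|
| z | 4.265 | 4.753 |
| Critical observed HR | 0.246 | 0.210 |
| P(cross) at HR 0.444, Schoenfeld drift 0.811 × 6.083/2 = 2.466 | 3.6% | 1.1% |
| P(cross) at HR 0.444, Freedman drift 6.083/2.6 = 2.340 | 2.7% | 0.8% |

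The chance of landing between the boundaries at the design effect was 3.6 − 1.1 = 2.5% (Schoenfeld) or 2.7 − 0.8 = 1.9% (Freedman).

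**3. Could sidedness explain the gap?** No. It accounts for a factor of 2, and the gap is a factor of 10. Two-sided, the values are z = 4.417 and 4.892, which are still different.

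**4. Effect on the final test.** The final critical value that keeps overall one-sided alpha at 0.05, with information fraction 0.5, is 1.644855 (nominal p 0.0499998) with the first level and 1.644854 (nominal p 0.0500000) with the second. The nominal levels differ by less than 0.0000002.

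**5. Where was the interim result?** The documents do not give the formula behind the stated conditional powers. Assume equal CHW weights (from 37/74), the observed trend, and a final critical value of 1.645. With n₂ second-stage events,

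CP = Φ( z₁√(n₂/37) + z₁ − 1.645√2 ).

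- 90% at 104 events, n₂ = 67: z₁ = (2.326 + 1.282)/(1 + 1.346) = 1.54.
- 75% at 69 events, n₂ = 32: z₁ = (2.326 + 0.674)/(1 + 0.930) = 1.55.

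The two agree. The one-sided p is about 0.06, and the observed HR about exp(−2 × 1.54/6.083) = 0.60.

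As a sensitivity check, weight by actual information, with t = 37/104 or 37/69 and z₁ = √t × [1.645 + Φ⁻¹(CP) × √(1 − t)]. This gives 0.596 × (1.645 + 1.282 × 0.803) = 1.59 and 0.732 × (1.645 + 0.674 × 0.681) = 1.54.

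**The case against.** The strongest reply is that the look is over and neither threshold came into play. Section 3.1.2 describes a sample-size adjustment made after the interim and reviewed by the IDMC, and section 3.2 reports a conditional power as observed. Under section 10.2 the number of events rises only in the promising zone, so a rise to 104 events is not what a boundary crossing would have produced. The final test is unaffected, and both levels amount to almost no chance of an early efficacy stop. All of this stands, and it limits the point to a correction of the record.

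Two further cautions also stand. Redacted lines sit close to the relevant text in the synopsis and section 10.2, and the SAP may state the boundary, so one can say only that readable text does not resolve the conflict. Even then, at least one of the two visible sentences would still need correcting. The values also differ by a single zero, and one is set in mathematical notation, so a digit lost or gained in reading the PDF cannot be fully excluded. There is no sign of this, and the source document will settle it.

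A reader might infer that the interim decision was compromised or that type I error control is in doubt. The documents do not support either inference: the implied interim z is far below both boundaries, and the final critical value is the same to five decimals.

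**Conclusion.** The inconsistency is real: one interim test of the primary endpoint has two significance levels, ten-fold apart, in current synopsis text. Its importance is minor. Had the interim result fallen at an observed hazard ratio between about 0.210 and 0.246, the two sentences would have given different answers. At the design effect that had a probability of about 2–2.5%.

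On the figures in section 3.2 it very probably did not happen. That conclusion rests on assumed weights and the observed-trend form of conditional power, though changing the weights moves the implied z only between about 1.54 and 1.59. The boundary comparison itself assumes one-sided levels and the usual log-rank approximations. What remains is that the protocol does not tell a reader which boundary was in force.

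**What to change.** The sponsor should take the boundary actually used from the design file or the IDMC record. It should then:

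- state that single value, with its sidedness, in the synopsis, replacing both present figures;
- state the same value in section 10.2 and check that the SAP agrees;
- report it in the study report as the alpha spent at the interim.

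The cost is one number and a cross-check. No sample size, event count, final critical value or analysis needs to change.

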CTL	Cytotoxic T Lymphocytes
CxCa	Cervix cancer
D	Day
DC	Dendritic Cells
DCR	Disease Control Rate
DL	Dose Level
DLT	Dose Limiting Toxicity
DNA	Deoxyribonucleic acid
DoR	Duration of Response
ECG	Electrocardiogram
ECOG	Eastern Cooperative Oncology Group
eCRF	Electronic Case Report Form
EGFR	Epidermal Growth Factor Receptor
EPP	Evaluable per Protocol Population
FACS	Fluorescence-activated cell-sorting
FDG-PET	Fluorodeoxyglucose Positron Emission Tomography
GCP	Good Clinical Practice
GMO	Genetically Modified Organism
HBV	Hepatitis B Virus
hCG	human Chorionic Gonadotropin
HCV	Hepatitis C Virus
HIV	Human Immunodeficiency Virus
HLA	Histocompatibility Leukocyte Antigen
HNC	Head and Neck Cancer
HPV	Human Papilloma Virus
HR	Hazard Ratio
IB	Investigator's brochure
ICF	Informed Consent Form
ICH	International Conference on Harmonization
ICMJE	International Committee of Medicinal Journal Editors
ICU	Intensive Care Unit
IDMC	Independent Data Monitoring Committee
IEC	Independent Ethics Committee
IFN	Interferon

IL	Interleukin
IM	Intramuscular
IMP	Investigational Medicinal Product
IND	Investigational New Drug
IO	Immuno-Oncology
IRB	Institutional Review Board
IRR	Infusion-Related Reaction
irAE	Immune-related Adverse Event
ISH	In Situ Hybridization
IU	International Unit
IUD	Intrauterine devices
IV	Intravenous
LDH	Lactate Dehydrogenase
LLN	Lower Limit of Normal
M	Month
MAD	Maximum Administered Dose
MDRD	Modification of the Diet in Renal Disease
MoAb	Monoclonal Antibody
ml	Milliliters
MTD	Maximum Tolerated Dose
MRI	Magnetic Resonance Imaging
MVA	Modified Vaccinia virus Ankara
NCI-CTCAE	National Cancer Institute's Common Terminology Criteria for Adverse Events. Also referred as CTCAE in the text
NK	Natural Killer
NOAEL	No Observed Adverse Effect Level
NSAID	Non-Steroidal Anti-Inflammatory Drug
ORR	Overall Response Rate
OS	Overall Survival
PBMC	Peripheral Blood Mononuclear Cells
PCR	Polymerase Chain Reaction
PD	Progressive Disease
PD-1	Programmed-Death 1
PD-L1	Programmed-Death Ligand 1
PHA	Phytohemagglutinin
PFS	Progression Free Survival
PFU	Plaque Forming Unit
PR	Partial Response
PS	Performance Status
Q2W	Every two Weeks
Q4W	Every four Weeks
RECIST	Response Evaluation Criteria In Solid Tumors
RNA	Ribonucleic Acid
RP2D	Recommended Phase 2 Dose
SAE	Serious Adverse Event
SAF	Safety Population
SC	Subcutaneous
SCCHN	Squamous Cell Carcinoma of Head and Neck
Sd	standard deviation
SD	Stable Disease
SUSAR	Suspected Unexpected Serious Adverse Reaction
TAA	Tumor Associated Antigen
TCR	Tumor Cross reactivity
TEAE	Treatment Emergent Adverse Event
TIL	Tumor Infiltrating Lymphocytes
TMF	Trial Master File
TPO	Thyroid Peroxidase
TO	Target Occupancy
ULN	Upper Limit of Normal

VIN

WBC

Vulvar Intraepithelial neoplasia

White Blood Cells

ABBREVIATIONS / DEFINITION OF TERMS (Cont.)

DEFINITIONS

Consented patient	A patient who has signed the informed consent form.
Screened patient	A patient identified during the pre-screening process as a candidate for entry into the study and who has signed the Informed Consent Form (ICF) to undergo procedures required to verify the eligibility criteria before inclusion
Screen Failure	Any patient who underwent screening procedures, and who is found to be not eligible for entry into study and therefore does not receive any study treatment.
Included patient	A patient who signed the ICF, has been included in the study and has received at least one administration of study treatments (TG4001 or avelumab).
Lost of follow-up patient	An included patient for whom no further news is obtained by the Investigator before the last study assessment. The date of lost of follow-up is the date the Investigator received the last news from the patient i.e. during a visit or a telephone contact or any written means.
Protocol deviation	All non adherences to following protocol requirements: study inclusion or exclusion criteria, conduct of the study, patient management or patient assessment.
Evaluable patients	
Evaluable patients for DLT determination: patients must complete the first 4 weeks of the combination or discontinue before the end of the 4 weeks for a DLT. Patients must receive at least one dose of both IMPs (TG4001 + avelumab) and have at least one valid post-baseline safety assessment.
 
Patients who are not evaluable for phase Ib safety analysis or are withdrawn for other reasons than toxicity, will be replaced.
 
Phase II part 1: Evaluable patients population for tumor response: patients who were dosed with both IMPs (TG4001 + avelumab) and have at least one baseline and one post-baseline evaluable CT-scan at week 6 after start of study treatment with a best overall response assessment different from 'Unknown' according to RECIST 1.1 evaluation criteria and have no major protocol violations or major dosing violations. Major dosing violation is considered when minimum exposure is not met, defined as at least 6 TG4001 injections and 3 avelumab administrations except if patient has progressed or died due to underlying disease before or at the first evaluation.
 
Phase II part 2: Full Analysis Set (FAS) which consists of all randomized patients who were administered at least one dose of IMP(s) according to the treatment allocated at randomization.

Start of study treatment	Corresponds to date of Day 1 for phase Ib and phase II part 1 and to date of randomization for phase II part 2
--------------------------	--

1 INTRODUCTION

1.1. Background and introduction

1.1.1. Human PapillomaVirus (HPV) and related diseases

Human papillomavirus (HPV) is the most common diagnosed sexually transmitted infection. It is associated with condyloma acuminata, anogenital (cervical, vaginal, vulval, penile, anal) squamous intraepithelial lesions and malignancies, and also squamous cell carcinoma of the head and neck (SCCHN).

HPV is a small deoxyribonucleic acid (DNA) virus of approximately 7900 base pairs. The HPV genome encodes DNA sequences for six early (E) proteins associated with viral gene regulation and cell transformation, two late proteins which form the shell of the virus, and a region of regulatory DNA sequences known as the long control region or upstream regulatory region (Palefsky J.M. and Holly E.A., 1995).

HPV genotypes can be broadly split into “high-risk” (16, 18, 31, 33, 35, 39, 45, 51, 52, 56, 58, 59 and 68) and “low-risk” (6, 11, 40, 42, 43, 44, 53, 54, 61, 72, 73 and 81) based upon their malignant potential. Types 16 and 18 are the most commonly isolated HPV types in cancer with type 16 found in approximately 50 % of patients with cervical cancer for example (de Sanjose S. *et al.*, 2010). However, not all infections with HPV type 16 or 18 progress to cancer. Furthermore, within single oncogenic HPV types, variants exist that are associated with different oncogenic potential (Hildesheim A. *et al.*, 2001). Beyond causing cervical cancer, HPV is also implicated in cancer of the anus (Tilston P., 1997) and penis (Varma V.A. *et al.*, 1991). There is also an approximately 2 to 3 fold increased risk for cancers of the oral cavity and oropharynx in patients infected with high-risk (oncogenic) HPV subtypes: HPV-16 genotype but also HPV-18, 31 or 33 (de Sanjose S. *et al.*, 2010), (Hildesheim A. *et al.*, 2001). HPV associated tumors predominantly arise in the base of the tongue or the tonsillar region, although a small percentage of tumors at other sites are also HPV positive. It is unclear why the oropharynx is more susceptible to HPV transformation than other sites.

Cohort studies from the 1990s suggested that approximately 50 % of oropharyngeal cancers were attributable to HPV, while more recent studies suggest that HPV may account for as much as 70 to 80% of these malignancies (Sturgis E.M. and Ang K.K., 2011), (Chaturvedi A.K. *et al.*, 2011).

A review on the published clinical trials, both single-arm and randomized, demonstrated HPV positivity ranging from 20 to 60% of oropharyngeal cancers (Ihloff A.S. *et al.*, 2010).

These data were confirmed in 2013 by a systematic literature review that assessed for Europe a 39.7% overall prevalence of HPV oropharyngeal cancer, demonstrating also a substantial increase over the time from 35.3% before year 2000 to 73.1% after year 2005 and a 23.7% overall prevalence of HPV non-oropharyngeal cancer, demonstrating also a substantial decrease over the time from 23.6% before year 2000 to 11.7% after year 2005 (Mehanna H. *et al.*, 2013).

1.1.2. Role of HPV in the carcinogenesis of SCCHN

Tumor carcinogenesis in SCCHN involves dynamic interactions among many factors. Exposure of the upper aerodigestive tract to alcohol or tobacco is one of the preponderant risk factors for SCCHN, and exposure to both increases the risk beyond what would be expected if the agents simply had additive effects (Cann C.I. *et al.*, 1985).

Another common risk factor is alteration of the function of the p53 tumor suppressor gene, which may be caused by either gene mutation or infection with an oncogenic type of human papillomavirus (HPV) (Brachman D.G. *et al.*, 1992), (Gillison M.L. and Shah K.V., 2001).

In some patients, particularly those with oropharyngeal cancer not associated with p53 mutation or the molecular impacts of alcohol and tobacco, HPV infection can cause head and neck cancer even in the absence of other molecular alterations (Haddad R.I. and Shin D.M., 2008), (D'Souza G. *et al.*, 2007). All of these risk factors are likely to result from and contribute to suppression of the patient's immune system, as is the tumor itself (Alhamarneh O. *et al.*, 2008).

Studies show that an infection with high-risk HPV is an independent risk factor for the development of SCCHN and needs to be considered along with the traditional risk factors such as tobacco abuse or alcohol (D'Souza G. *et al.*, 2007), (Gillison M.L. *et al.*, 2000b).

HPV-16 is the far most common type detected in oropharyngeal cancer accounting for 90–95% of the HPV positive tumors (Marur S. *et al.*, 2010), (Kreimer A.R. *et al.*, 2005). High-risk HPVs produce 2 oncoproteins, E6 and E7, which are necessary for viral replication through their proliferation stimulating activity and play a key role in malignant transformation. The E6 oncoprotein binds and induces the degradation of the p53 tumor suppressor protein via an ubiquitin-mediated process disrupting the p53 pathway which leads to uncontrolled cell cycle progression (Chung C.H. and Gillison M.L., 2009), (Havre P.A. *et al.*, 1995). The HPV E7 protein binds and degrades the retinoblastoma protein (pRb), preventing it from inhibiting the transcription factor E2F resulting in loss of cell cycle control. Furthermore, the functional inactivation of Rb results in upregulation of the p16-protein. P16 is encoded by the CDKN2A tumor suppressor gene and regulates the activity of Cyclin D-CDK4/6 complexes that phosphorylate Rb leading to release of the transcription factor E2F which initiates cell cycle progression. HPV-positive tumors are characterised by high expression of high levels of p16 (Nevins J.R., 2001). The p16 protein can be detected by immunohistochemistry, and since several studies have shown a very high correlation (> 90%) to HPV-positivity in oropharyngeal tumors, it has been suggested as a clinically useful surrogate marker (Mellin Dahlstrand H. *et al.*, 2005), (Klussmann J.P. *et al.*, 2003)

In head and neck cancer caused by the traditional risk factors, tobacco and alcohol, p53 is commonly mutated (Ahmadegbe J.C. *et al.*, 1995), (Carlos de Vicente J. *et al.*, 2004) and 9p21-22 is lost early in carcinogenesis resulting in the loss of the tumor suppressing gene p16 (Kim S.H. *et al.*, 2007). In contrast, HPV-positive head and neck tumors have decreased expression of wild-type p53 due to the inactivation and degradation by the E6 oncoprotein.

